10 minutes after receiving the Secretin or placebo, the attending surgeon will examine the anastomosis or repaired cut edge of the pancreas to determine if leakage of pancreatic fluid is noted, leak location(s), type (side branch/main duct), color of the fluid and whether any further intervention was performed in an effort to close the leak. Specifics of operative intervention will be documented. The patient will then undergo standard surgical closure of the abdomen.

As is standard of care at DHMC, surgical drains will be placed adjacent to the anastomosis and drain amylase output will be checked on POD #1 through POD#5. Pancreatic leak is defined according to the International Study Group of Pancreatic Fistula (ISGPF) definition as a clinically relevant postoperative pancreatic fistula is now redefined as a drain output of any measurable volume of fluid with an amylase level >3 times the upper limit of institutional normal serum amylase activity, associated with a clinically relevant development/condition related directly to the postoperative pancreatic fistula. Randomization assignments will be revealed once the patient has been discharged from the hospital following their initial surgical intervention. A follow-up visit with the patient two weeks following discharge, will evaluate for any evidence of ongoing pancreatic duct leak.

The patient will also be followed for thirty (30) days after secretin/placebo administration by the research team to assess for a pancreatic leak and sequelae of a leak, - intra abdominal deep soft tissue infection, surgical site infection, hemorrhage, IR (interventional radiology) drain placement, or reoperation. This will be accomplished by telephone and/or by chart review Patients discharge date will be followed for the study. If no secretin/placebo is administered, the patient will not be followed on the study.

If any of the above are noted during the 30 days following secretin/placebo administration the following will be used to assess causality:

Causality

The following 4-point scale will be used for rating the causal relationship of the AE to the investigational product:

Unrelated: Clearly and incontrovertibly due to extraneous causes, and does not meet criteria listed under unlikely, possible, or probable.

- Unlikely:** Does not follow a reasonable temporal sequence from administration. May have been produced by the patient's clinical state or by environmental factors or other therapies administered.

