- Possible:** Follows as reasonable temporal sequence from administration. May have been produced by the patient's clinical state or by environmental factors or other therapies administered.
- Probable:** Clear-cut temporal association with improvement or cessation of test drug or reduction in dose. Reappears upon re-challenge. Follows a known pattern or response to test drug.

The primary outcome of interest will be the presence of pancreatic leaks based on the amount of drain amylase on or after POD#3. Secondary outcomes will include: 1) technical interventions intraoperatively directed to leak closure or manipulation of the anastomosis following Secretin or placebo stimulation 2) length of stay as a surrogate to complication severity after pancreatic surgery.

Patient demographics, risk factors, operative technique, randomization assignment and outcome data will be recorded on standard case report forms – **See Case Report Forms in Appendix**. Data will be stored in an encrypted hard-drive by a single agent ([name]) who is the only researcher who has access to the randomization data.

5. Inclusion/Exclusion Criteria:

Please provide detailed description of inclusion and exclusion criteria. If a formal protocol for the study exists, page references to the protocol are acceptable.

Inclusion criteria:

1. Scheduled for pancreatic surgery requiring pancreatic resection at DHMC
2. Age greater than 18 years old
3. Ability to provide written informed consent

Exclusion criteria:

1. Inability to provide written informed consent
2. Current ongoing acute pancreatitis
3. Pregnant or nursing mothers
4. Any medical condition which in the judgment of the Investigator renders participation in this study medically inadvisable.
5. Participation in an investigational clinical study for a drug or medical device within 30 days prior to Visit 1.
6. [Any known allergy to methylene blue.](#)

6. Financial Considerations:

Disclosure of financial impact on the participant is critical to informed consent. Insurance cannot be billed for research-related services outside the standard of care or paid for by the funding agency for

the study. The department, the study or the participant may be responsible for payment for research-related services. Participants should know which tests, visits, or procedures will be billed to them or their insurance and which ones will be paid by the funding agency for the study or the department.

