
The co-heads of the DSMB will be [name] and [name], in the Section of General Surgery and Gastroenterology and Hepatology. Drs. [name] and [name] will not be participating in the trial.

9. Genetics:

Does any part of the study involve genetic analysis of biological specimens?

Yes No

*If yes, respond to **Genetics Attachment C***

10. Instruments:

Describe each instrument, if any, used to collect data in this study.

Please see the CRF included in the appendix.

11. Deception.

Will deception of participants, including withheld information, be used in this research?

Yes No

If yes, complete a-d.

12. Enrollment:

a) Estimated number of participants for duration of entire study:

*At Dartmouth or associated sites: **Female: 88 Male: 88***

If Multi-center study: Estimated total number at all sites: 0

b) Estimated age range of participants: Age >18

13. Timetables:

a) Indicate length of participant involvement in the study:

Participation will involve enrollment at the time of surgery and discharge following surgery. Patients will then be seen in the clinic two weeks following the procedure.

*b) Estimate how long it will take to enroll enough participants to complete this study: At DHMC, approximately 120 major pancreas surgeries are performed annually. If 80% of patients agree to participate in the study, the enrollment should be complete after **24 months**.*

14. Risks:

The purpose of this section is to determine if subjects will be placed "at risk," which in general means exposed to the possibility of physical, psychological, social, economic, legal, dignitary or other harm as a consequence of any activity proposed in the research project.

a) What is the overall risk classification of the research?

- Minimal
- Greater than minimal
- Significant
- Unknown

Note: In the federal regulations on human subjects protection minimal risk means "The probability and magnitude of harm or discomfort anticipated in the research are not greater in and of themselves than those ordinarily encountered in daily life or during the performance of routine physical or psychological examinations or tests."

b) Describe any potential risks (physical, psychological, social, legal, economic, or other) and assess their likelihood and seriousness. Describe the procedures for protecting against or minimizing these risks, including risks to confidentiality, and assess their likely effectiveness. Please list risks from most severe/likely to least severe/unlikely.

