Attachment B
Placebo or Procedures that are Inconsistent with the Standard of Care

Consider the ethical implications of using a placebo or procedures that are inconsistent with the standard of care in this study. Specifically, explain what "standard of care" therapy is for this participant population and how the use of placebo therapy may affect risks for participants. Also discuss:

- a) the safety and efficacy of other available therapies (if any),*
- b) the maximum total length of time a participant may receive placebo on study,*
- c) the greatest potential harm that may come to a participant as a result of not receiving effective therapy (immediate or delayed onset), and*
- d) safeguards for the participants receiving placebo.*

Required comment from the local research team specifically addressing a-d above and in addition to any justification included in the study protocol. Information copied directly from the protocol is not acceptable in this section:

At this time, in average risk patients, we are unclear of giving Secretin intra-operatively will allow better identification and repair of pancreatic duct leaks. The drug is used occasionally in high risk patients to evaluate for duct leaks and we would like to see if this drug is universally useful in all patients undergoing pancreatic surgery. The patient will only be included in the study from the time of their surgery to initial hospital discharge. The risk of not receiving therapy is that they may have a higher risk of duct leak (we will know better after the study). Patients receiving placebo will receive the same standard of care post-operatively than those receiving Secretin stimulation.

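### The plan contradicts itself on how long patients are watched for a leak, and the primary endpoint has an opening day but no closing day

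*Combined protocol and SAP*

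**What the plan says.** Four time points bear on the end of observation.

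- Section 4 (Design, procedures, materials and methods), clinic visit: "A follow-up visit with the patient two weeks following discharge, will evaluate for any evidence of ongoing pancreatic duct leak".
- Section 4, surveillance by telephone and/or chart review: "The patient will also be followed for thirty (30) days after secretin/placebo administration by the research team to assess for a pancreatic leak". The sequelae listed include infection, hemorrhage, radiological drain placement and reoperation.
- Section 13a (Timetables), under length of participant involvement: "Patients will then be seen in the clinic two weeks following the procedure". The 30 days are not mentioned there.
- Attachment B: "The patient will only be included in the study from the time of their surgery to initial hospital discharge".

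Section 4 gives the primary outcome as the "presence of pancreatic leaks based on the amount of drain amylase on or after POD#3". The abstract and Section 2 use the same opening day, and none of the three gives a closing day. Section 7a names the leak definition without a time frame, and Section 7b names the Fisher test without one.

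The scheduled measurement is narrower: "drain amylase output will be checked on POD #1 through POD#5". The definition in Section 4 also requires a clinically relevant condition related to the fistula, with no time limit. Section 4 reveals the assignment once the patient has been discharged.

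**The concern.** The primary endpoint is a yes/no leak status compared by Fisher's exact test. Each patient's status depends on the period over which a leak may be counted, and the plan does not fix that period. Suppose a patient has a raised drain amylase on POD 3, goes home, and returns on day 20 for a radiological drain. Under Section 4 that event is captured. Under Attachment B the patient has already left the study. Two analysts following different sections could classify this patient differently.

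The second difficulty is that a window ending at discharge, or a set time after it, is longer for patients who stay longer. Length of stay is a secondary outcome, and Section 7a expects leak severity to lengthen it. The observation period would then depend on something the leak, and possibly the treatment, can change. If stays were shorter in one arm, that arm would be watched for less time and would have less chance of a late leak being recorded.

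**Working it through.** **Which statements truly conflict.** Attachment B limits inclusion to the initial stay, while Section 4 asks for surveillance to day 30. For any stay shorter than 30 days both cannot be followed. The two-week visit is timed from discharge in Section 4 and from the procedure in Section 13a. These give different days for every patient with a stay above zero, and for a stay longer than 14 days the Section 13a visit would fall before discharge. Section 6a mentions a two-week visit without an anchor, so it does not settle the matter.

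**Which statements can coexist.** Section 4 adds the 30-day follow-up to the clinic visit with the word *also*. A visit plus surveillance to day 30 is a coherent schedule. There are therefore four time points but two real conflicts: discharge against day 30, and the anchor of the visit.

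**Where each time point falls.** Let L be the length of stay in days, counted from surgery and infusion on day 0. The documents give no typical L, so the values below are assumptions.

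| L (assumed) | Discharge: L | Procedure + 14 | Discharge + 14: L + 14 | Infusion + 30 |
|---|---|---|---|---|
| 7 | 7 | 14 | 21 | 30 |
| 10 | 10 | 14 | 24 | 30 |
| 16 | 16 | 14 | 30 | 30 |
| 21 | 21 | 14 | 35 | 30 |

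If each were used as the end of observation, then against day 30:

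- Discharge stops 30 − L days early: 23 days at L = 7, 9 days at L = 21.
- Procedure + 14 stops 30 − 14 = 16 days early for everyone.
- Discharge + 14 stops 16 − L days early when L is below 16 (9 days at L = 7) and runs past day 30 when L is above 16 (5 days over at L = 21).

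Two of the four vary with length of stay: discharge and discharge + 14.

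**Which part of the endpoint is affected.** Scheduled amylase covers POD 1 to 5, so the scheduled values inside the endpoint's window are those of POD 3, 4 and 5. No section makes POD 5 the endpoint's end. Follow-up to day 30 schedules no drain amylase. The missing closing day therefore matters mainly for the clinical-relevance component, for the sequelae, and for any drain amylase obtained later for clinical reasons.

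**The plan's sample size.** Inputs from Section 7c: 20% against 5%, two-sided alpha 0.05, 80% power.

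- Mean proportion 0.125.
- Uncorrected n = [1.960 × √(2 × 0.125 × 0.875) + 0.842 × √(0.20 × 0.80 + 0.05 × 0.95)]² / 0.15² = (0.917 + 0.383)² / 0.0225 ≈ 75.1, so 76 per arm.
- With continuity correction, (75.1 / 4) × [1 + √(1 + 4 / (75.1 × 0.15))]² ≈ 88 per arm.

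The plan's 88 per arm (176 in total) is reproduced. Section 7c attaches no observation window to the 20% and 5% rates.

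**The case against.** The strongest reply is that Section 4 is the methods section and already sets a fixed 30-day follow-up for everyone, with leak assessment as its stated purpose. Attachment B is a placebo-ethics form, not an outcome schedule, and Section 13a describes a visit without saying that data collection stops there. On this view only inconsistent administrative wording remains. Much of this stands: Section 4 is the natural governing text, and it is why the repair is cheap. But Attachment B states its limit without qualification, Section 13a answers the question about length of participation without mentioning 30 days, and Section 4 itself never says that a leak found by day 30 counts in the primary analysis. It ties the 30-day events to an adverse-event causality scale.

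A second reply is that the endpoint rests on drain amylase, which is scheduled only to POD 5, so the end of follow-up hardly matters. That stands for the scheduled amylase values. It does not stand for the clinical-relevance component in Section 4's own definition.

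A reader might infer four mutually exclusive ends of follow-up. The documents do not support that, because Section 4's visit and surveillance coexist. A reader might also infer a loss of power. If 10%, 20% or 30% of leaks were missed equally in both arms, the rates would become 18% and 4.5%, 16% and 4%, or 14% and 3.5%, and exact Fisher power at 88 per arm would fall from 83.8% to 78.6%, 72.1% or 63.9%. These are illustrations only. The documents give no missed share and no window for the planning rates. If those rates already refer to the window used, nothing is lost. Equal proportional loss also does not model the length-of-stay mechanism.

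**Conclusion.** The concern holds in a limited form. There are two direct contradictions (inclusion to discharge against follow-up to day 30, and the anchor of the two-week visit) and a primary endpoint with no closing day. If the discharge rule were followed, leaks becoming evident later would be missed, with observation ending 23 days before day 30 at an assumed stay of 7 days. Any discharge-anchored window would also differ between patients according to length of stay.

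The effect on the leak counts cannot be sized from the documents. Whether the arms would be watched for different lengths of time depends on whether stays differ between them, which is not known in advance. No power loss is established, and the sample size is not in error on this point. The matter should be corrected before analysis because it determines which events enter the primary comparison.

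**What to change.** Reconcile Section 4, Section 13a and Attachment B to one fixed outcome window for every patient, POD 3 to day 30 after infusion, and write that window into the primary endpoint in the abstract and Sections 2, 4 and 7a. State the closing rule for each component:

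- The amylase criterion uses the scheduled POD 3 to 5 values plus any later drain amylase obtained for clinical reasons.
- The clinical-relevance component and the sequelae are counted to day 30.

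Give the two-week visit a single anchor, and say that it is a contact within the window and not its end. State in Section 7c that the 20% and 5% rates are taken to refer to this window.

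The 30-day telephone or chart review is already planned, so no visit or test is added. The downside concerns blinding. Assignments are now revealed at discharge, so events counted afterwards would be assessed unblinded. The reveal should move to after day 30, and the two changes should be made together. The cost is a later reveal for patients discharged before day 30: at least 23 days later at an assumed 7-day stay.

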Attachment B
Placebo or Procedures that are Inconsistent with the Standard of Care

Consider the ethical implications of using a placebo or procedures that are inconsistent with the standard of care in this study. Specifically, explain what "standard of care" therapy is for this participant population and how the use of placebo therapy may affect risks for participants. Also discuss:

- a) the safety and efficacy of other available therapies (if any),*
- b) the maximum total length of time a participant may receive placebo on study,*
- c) the greatest potential harm that may come to a participant as a result of not receiving effective therapy (immediate or delayed onset), and*
- d) safeguards for the participants receiving placebo.*

Required comment from the local research team specifically addressing a-d above and in addition to any justification included in the study protocol. Information copied directly from the protocol is not acceptable in this section:

At this time, in average risk patients, we are unclear of giving Secretin intra-operatively will allow better identification and repair of pancreatic duct leaks. The drug is used occasionally in high risk patients to evaluate for duct leaks and we would like to see if this drug is universally useful in all patients undergoing pancreatic surgery. The patient will only be included in the study from the time of their surgery to initial hospital discharge. The risk of not receiving therapy is that they may have a higher risk of duct leak (we will know better after the study). Patients receiving placebo will receive the same standard of care post-operatively than those receiving Secretin stimulation.

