C) This would be a randomized, double-blind, placebo controlled trial. 1/2 of the patients would receive intra-operative secretin, the other half would receive saline placebo. Both the surgeon and patient would be blinded to the randomization assignment. The advantage of giving secretin would be that it may allow for the identification of a leak intra-operatively and subsequently allow for repair if the leak was identified prior to abdominal wall closure. While the safety profile of the drug is excellent, receiving the medication could theoretically cause an increased intraductal pressure which may cause a leak when one was not already present.

D) Human subjects are needed to evaluate intra-operative, intravenous secretin in patients undergoing pancreatic duct resection.

4. Design, procedures, materials and methods:

Use a level of detail similar to what would be used when submitting an article for publication in a peer reviewed journal. Explain the study procedures, data collection, and analysis process. Please define terms and explain concepts which might be confusing to reviewers who are not expert in the area of the study. If a formal protocol for the study exists, page references to the protocol are acceptable.

This study design is a prospective, double-blind, randomized-controlled trial. We will enroll patients in our institution undergoing pancreatic resection to receive either 1) one dose weight-based Secretin to be given once the closure of the pancreatic resection margin is complete 2) saline placebo.

Consent and basic demographics will be garnered by the physician in an office visit once the surgery has been scheduled and consent for the surgery is being obtained. The consent will be validated by the treating surgeon in the pre-procedure area on the day of the surgery.

The patient will undergo the scheduled surgery. Once the pancreatic anastomosis has been deemed acceptable by the attending physician, but prior to abdominal closure, the patient will be randomized to receive either Secretin (0.2 mcg/kg) or saline placebo. The attending surgeon will be blinded to this assignment.

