CRF, and then building a multivariable logistic regression model using the categorical variable of drain amylase >3x the upper limit of normal. The data from the multivariate regression will be reported as Odds Ratios.

The secondary outcomes are both categorical and continuous variables and thus we will use the Fisher's Exact test as well as the two-tailed student's t-test. A multivariable analysis is not planned for evaluating the secondary variable.

Randomization will occur in a block format of 5 and will be generated by the primary investigators.

c) Justify the sample size, using the concepts of power, type I error, and effect size if applicable. If a formal protocol for the study exists, page references to the protocol are acceptable.

A clinically significant absolute decrease of 15% (20% to 5%) in the pancreatic duct leak rate. Based on these estimates and a two-tailed test comparing proportions using the statistical calculator (<http://homepage.stat.uiowa.edu/~rlenth/Power>), we project an estimated sample size of **176 participants (88 per arm)** to demonstrate an absolute 15% reduction in the leak rate with 80% power at a two-sided alpha level of 0.05.

8. Data and Safety Monitoring:

Describe plans for data and safety monitoring to ensure the safety of subjects and the quality of the data. As described in federal guidance "... a variety of types of monitoring may be anticipated depending on the nature, size, and complexity of the trial. In many cases, the principal investigator would be expected to perform the monitoring function." This plan should include monitoring to determine:

The progress of the trial, including periodic assessments of data quality and timeliness, participant recruitment, accrual and retention, participant risk versus benefit, and other factors that can affect study outcome. Monitoring should also consider factors external to the study when interpreting the data, such as scientific or therapeutic developments that may have an impact on the safety of the participants or the ethics of the study.

Note: This section does not request information related to sponsor study monitor visits. This section requires a description of an adequate data and safety monitoring plan.

Interim analysis will be performed once 50% (88) patients have been enrolled. If more than 66% of cases of duct leak are in a particular study group, a formal comparison between groups will be performed with the use of a two-sided stopping boundary of 0.005%.

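### Saline may not fully mask secretin from the surgeon who looks for its expected effect, and nothing keeps that finding from those who judge the leak

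*Combined protocol and SAP*

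**What the plan says.** Section 3C (Introduction) states the blind: "Both the surgeon and patient would be blinded to the randomization assignment". Under section 4, study drug is given only after the attending physician has accepted the anastomosis. Ten minutes later, "the attending surgeon will examine the anastomosis or repaired cut edge of the pancreas to determine if leakage of pancreatic fluid is noted". The surgeon also notes where the leak is, its type and colour, and any further repair.

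The rationale in sections 1 and 3B is that secretin makes leaks visible before closure. Section 3B says the site has used it occasionally for this purpose since 2011. Attachment B agrees: "The drug is used occasionally in high risk patients to evaluate for duct leaks".

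On the outcome, section 4 defines a leak as drain amylase above three times the upper limit of normal, "associated with a clinically relevant development/condition related directly to the postoperative pancreatic fistula". Section 7a also points to the ISGPF definition. Sections 1 and 2, the outcome paragraph of section 4 and the regression in section 7b rest on drain amylase. Length of stay is a secondary outcome.

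Section 4 reveals assignments at hospital discharge. It also plans a clinic visit two weeks after discharge and has the research team follow each patient for leak and its sequelae to day 30. In answer to the form's question about safeguards for placebo participants, Attachment B says: "Patients receiving placebo will receive the same standard of care post-operatively than those receiving Secretin stimulation".

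**The concern.** A placebo masks the syringe; it does not mask a response that the observer is asked to look for. The margin has just been accepted, so new fluid after the infusion is what the hypothesis predicts for secretin more than for saline. A surgeon who sees it has some information about the arm, even if no assignment is ever disclosed.

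Seeing and repairing the leak is the intervention's mechanism and is not bias. What is at stake comes later: whether a fever, collection or drain placement is attributed to a fistula, and when the patient goes home. If the people making those calls know the operative finding, or after discharge the assignment itself, their calls can differ by arm for reasons other than the drug's effect. The direction is not predictable. A repaired leak may be discounted as dealt with, or the patient may be regarded as a known leaker.

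**Working it through.** **The plan's own figure.** Section 7c gives the effect as "A clinically significant absolute decrease of 15% (20% to 5%) in the pancreatic duct leak rate", "with 80% power at a two-sided alpha level of 0.05", and 88 patients per arm. The two-proportion formula gives [1.960·√(2·0.125·0.875) + 0.842·√(0.20·0.80 + 0.05·0.95)]² / 0.15² ≈ 75.1 per arm, or 76 rounded up. With the continuity correction this becomes 88 per arm, 176 in total, so the stated size is reproduced. Exact two-sided Fisher power at 88 per arm is 83.8%, and the actual type I error at 20% in both arms is 3.2%. The point below does not change the sample size.

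**How strong is the cue?** Let s and c be the proportions with visible fluid on secretin and on saline. Both are assumptions, as the documents give neither. With 1:1 allocation:

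- P(secretin | fluid seen) = s/(s + c)
- P(saline | no fluid seen) = (1 − c)/(2 − s − c)

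For s = 20% and c = 2%, these are 0.20/0.22 = 91% and 0.98/1.78 = 55%. Expected numbers with fluid are 88 × 0.20 = 17.6 and 88 × 0.02 = 1.8.

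| s | c | P(secretin, fluid seen) | P(saline, no fluid) | Fluid seen, of 88 each |
|---|---|---|---|---|
| 20% | 2% | 91% | 55% | 17.6 v 1.8 |
| 10% | 5% | 67% | 51% | 8.8 v 4.4 |
| 40% | 0% | 100% | 63% | 35.2 v 0 |
| 20% | 15% | 57% | 52% | 17.6 v 13.2 |
| 60% | 5% | 92% | 70% | 52.8 v 4.4 |

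The cue ranges from weak to near certain. Unless s is high, it sits mainly in patients with visible fluid.

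**Which outcomes can it reach?** Amylase is a laboratory value checked on days 1 to 5 in every patient, normally before the reveal, so it is little exposed. The clinical clause of the section 4 definition is a judgement, and discharge timing is a decision; both are exposed. The text gives no masked assessor for either. The two-week visit comes after the reveal, as does any part of the 30-day follow-up and causality rating that falls after discharge.

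**What could a shift do?** These are illustrations with assumed shifts, and they apply only if the clinical clause is part of the endpoint.

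- One patient in 88 is 1.1 points. Two or three altered attributions in one arm move the difference by 2/88 = 2.3 or 3/88 = 3.4 points, against a design effect of 15.
- No true effect, 20% in both arms: if 10% of secretin-arm leaks go uncalled (20% v 18%), Fisher rejection rises from 3.2% to 4.2%. If 25% go uncalled (20% v 15%), it rises to 10.1%.
- True rates of 20% v 5%: two points of extra leak calls on secretin (20% v 7%) cut power from 83.8% to 66.5%.

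**The case against.** The strongest reply is that most statements of the primary outcome measure it by drain amylase, which a guess about the arm hardly touches. That stands. The exposure of the primary outcome depends on the clinical clause in section 4 and the ISGPF reference in section 7a. The documents need to be reconciled on this; until they are, the judgement component cannot be set aside.

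Three stronger readings are tempting, and the documents do not support them.

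- A reader might infer that saline cannot mask secretin and that the blind fails. The inspection is the same in both arms, section 3B calls the evidence anecdotal, prior use was occasional, and Attachment B says the benefit is unclear. The cue is probabilistic.
- A reader might infer that patients with visible fluid are the ones most likely to reach the primary outcome. Suppose 20% have a leak and secretin reveals 75% of those: 0.20 × 0.75 = 15 points. If all are repaired, 5% remain, which is the design rate, and those leaks are in patients in whom no fluid was seen. The inference needs repairs that often fail, which the documents do not say.
- A reader might infer that Attachment B makes equal care depend on the surgeon's blind. It says only that placebo patients receive the same standard of care. It names no mechanism, and the link to blinding is not in the text.

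Some protection does exist. Section 4 limits the randomization data to one researcher, and section 14b restricts access to the case report form. Neither keeps the operative finding from the surgeon or the ward. The case report form itself is not available, so its layout cannot be checked.

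**Conclusion.** The concern holds in a limited form. If secretin works as hypothesised, visible fluid is a cue to the arm, and the person who sees it is the one meant to be blind. No section masks those who judge the leak to that finding, and the reveal at discharge discloses the assignment before some assessments are complete. The exposed items are the clinical component of the leak definition and length of stay; an endpoint based on amylase alone would be little affected.

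Neither the size nor the direction can be fixed from the documents. The cue is 57% to 100% informative across the assumed rates shown, and each altered attribution is worth about 1.1 points. This is a gap worth closing because closing it is cheap. It does not show that the result will be biased, and it leaves the sample size unchanged.

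**What to change.** In section 4:

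- State that leak status, including whether a clinical condition is directly related to the fistula, is coded by existing research staff who have no access to the randomization list. They should work from drain amylase results and post-operative records with the operative findings withheld. Withholding one sheet is not enough if the repair is described elsewhere in the record they read.
- Keep the ten-minute inspection and repair data on a separate form.
- Delay the routine reveal of assignments until that patient's 30-day leak coding is locked. Without this, coders could learn the actual arm at discharge.

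Optionally, have the surgeon record a guess of the arm straight after the inspection. It should be reported descriptively only, because a correct guess is confounded with the drug's effect.

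The cost is extra form handling, preparing records with operative findings removed, a later routine reveal, and an adjustment to the single-person access in sections 14b and 27c if the coders are other people. No new patients or procedures are needed. Discharge decisions remain open to influence, so length of stay should be interpreted with that in mind.
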